Will Be Viewed Name, Social Security Number, Medical

Record Number, Address by street

location, Telephone number, Geographical Subdivisions Smaller Than a State, All Elements of Dates for Dates Directly Related to an Individual (i.e., Birth Date, Admission Date, Discharge Date), Email

Address

Will Be Recorded Name, Social Security Number, Medical

Record Number, Address by street location, Telephone number, Geographical Subdivisions Smaller Than a State, All Elements of Dates for Dates Directly Related to an Individual (i.e., Birth Date, Admission Date, Discharge Date), Email

Address

Data Collection Sheet

A Data Collection Sheet is required if you are either performing a retrospective review, or your study meets the category of exempt 4 research, or your study meets the category of expedited 5 research. Please upload it here.

Data Collection Source(s) Participant, Medical Chart (Paper or

Electronic)

18. Data - HIPAA

Obtaining HIPAA Authorization Yes

How PHI Will Be Protected from Improper Use or Disclosure

No

Study data will include no direct identifiers, and a unique number assigned to each patient. Study data will be kept in a locked filing cabinet in the PI's office, and kept separate from the subjects' signed consent forms (also in a locked cabinet). A list of subject-number pairings will also be in a locked filing cabinet, and only the PI and the study team will be assess to these cabinets.

PHI Will Be Destroyed at the Yes Earliest Opportunity Consistent with the Research

When and How PHI Will Be Destroyed

PHI will be destroyed at the completion of the study by shredding documents with PHI, which are otherwise in locked filing cabinets. The key linking the study data (in RedCap) to PHI (e.g., consent forms) will be destroyed at the end of the study, so that PHI (and patient identities) cannot be linked back to the study data. Only the de-identified study data will be needed for publication. Signed consent forms with HIPPA waivers (unlinked to data) will be kept for six years following completion of the study, and then destroyed via shredding.

PHI Will Be Shared

PI must attest to the following.

Data will be stored in a locked filing cabinet located in a locked closet, within a locked office (PI: [name]). Each lock has a separate key. Only two persons have the key to the filing cabinet: [name] (PI) and the study research coordinators. Data files will be kept separate from identifiable data (PHI), with the exception of a password protected and encrypted Excel file linking subject names and subject numbers. This file will be located on a ISMMS network drive and only accessed from ISMMS computers. Only [name] and the coordinators will have the password. Raw data files may be retrieved by [name] or the research coordinator, and viewed on site in a private office space. Files will not be removed from Mount Sinai Hospital. Files will be immediately returned to their secure location within the filing cabinet.

Power Analysis/Data Analysis Plan (Including Any Statistical Procedures)

[name] will lead statistical analyses, which will consist of dependent T-tests comparing differences in outcomes (e.g., memory composite score) between the drug and placebo phases of the cross-over trial.

20. Data - Safety Monitoring

More Than the Minimum Data Yes Safety Monitoring Will Be Done

Principal Monitor [name]

Additional Monitors

Specific Items That Will Be Monitored for Safety

Suicidal ideation will be monitored with the Columbia Suicide Severity Rating Scale. Subjects who report suicidal ideation at any point in the study will be escorted to the psychiatric emergency department at Mount Sinai Hospital for further evaluation.

Suicidal ideation and other adverse events reported by patients will be recorded. Co-I [name] [name]. will review all adverse events as they are reported, and judge severity. [name] is not involved in data collection or processing, so she can be unblinded to identify whether adverse events occurred during atomoxetine or placebo.

Frequency of Data Review

Suicidal ideation will be evaluated at baseline, first follow-up, and second follow-up for all subjects, and immediate action will be taken if suicidal ideation is present (as noted above).

[name] will also be told immediately of any other serious adverse events, such as allergy to atomoxetine. She will have access to condition assignments in the case of adverse events.

Rules for Alteration of Study Design

After twelve subjects have been completed the trial, [name] will evaluate whether serious adverse events are more likely during atomoxetine or placebo. If serious adverse events are 2:1 more likely during atomoxetine, the study will be halted.

Selection Procedures to Minimize Toxicity

We are using the recommended dosage of atomoxetine based on prescribing information in the package insert. Also, we are excluding patients taking strong CYP2D6 inhibitors (e.g., paroxetine, fluoxetine, quinidine), which minimizes risk of toxicity.

Grading System to Evaluate Adverse Events

Serious adverse events will include suicidal ideation and allergy to atomoxetine.

Other adverse events include constipation, upset stomach, difficulty sleeping, dry mouth, loss of appetite, irregular periods, decrease in sexual function, urinary hesitancy sweating, and dizziness.

Procedures to Assure Data Accuracy

All adverse events reported to the research team at any time in the study (including the three assessment phases) will be recorded for frequency and severity. Severity will be judged my our study physician, [name] [name]. These will be documented in a study RedCap database, and will be reported for each condition (atomoxetine, placebo) with the study results. [name] will also be able to determine subject condition in the event of serious adverse events.

Suspension Reported to

Suspension would be reported the the IRB.

Anticipated Circumstances of Subject Withdrawal

Subjects would be withdrawn from the study if they experience any severe adverse events. Of course, subjects may choose to withdraw at any time without penalty.

Primary or Secondary Safety Endpoints

Primary safety outcome will be suicidal ideation.

Secondary safety endpoints include constipation, upset stomach, difficulty sleeping, dry mouth, loss of appetite, irregular periods, decrease in sexual function, urinary hesitancy sweating, dizziness, and allergy to atomoxetine.

Data Monitoring Committee Description

DMC.docx

DMC Charter Available

21. Funding

Funding Source Name National Multiple Sclerosis Society

Contact

Funding Category Foundation

Meditrack (https://contracts.tractmanager.com/Contracts/Login.aspx)

Grant or Contract Title Pilot Randomized Controlled Trial of Atomoxetine to Treat Memory Impairment in MS

Patients

Grant or Contract

Number

PP-1606-24739

Funding Status Funded **Project Initiated By** Investigator

Grant / Contract Principal [name]

Investigator (PI)

Department Neurology **Department** Neurology

Phone

Email [contact]

Protocol and Funding Proposal Match

No

Identify Substantive Differences Between Protocol and Funding

We changed the trial from a parallel design to a cross-over design to improve statistical power. As such, we lowered our sample size from 30 to 24. All other aspects (e.g.,

hypotheses, doses, outcomes, etc.) are the same.

Proposal

22. Drugs / Biologics

Study Fund Account (or alternate departmental / fund account, if study is not yet established)

Select One:

A fund number is required before the IDS will sign off on any forms or initiate any procedures. For those studies which an alternate departmental fund number is provided, IDS will delay billing by 6 months.

Add all drugs and biological agents whose use is specifically prescribed in the research. This includes approved drugs that are supplied or paid for by the company for this research, approved drugs that are not given under routine care guidelines, and all investigational drugs. Approved drugs whose use is up to the discretion of an attending physician as part of medical care do not need to be added. Contact the Investigational Drug Service (IDS) if unsure http://www.mssm.edu/ids.

To be completed by Pharmacy staff upon review of the protocol:

FYI: NO ACTION REQUIRED
IDS FEE SCHEDULE
Review:
Initiation:
Dispensation:
Maintenance:
Special Compounding:
Coordinating Center:
Close-Out:

23. Financial Administration

This information will help the Financial Administration of Clinical Trials Services (FACTS) office determine whether a Medicare Coverage Analysis (MCA) is needed for the research study. If you have any questions while completing this form, please contact the FACTS office at [contact] or [contact].

Clinical Research Study Category Investigator Initiated

Payment Options:

- * Option 1: No protocol-required services will be billed to patients or third-party payers. Does Not Need MCA
- * Option 2: Protocol-required services (i.e., routine care services) will be billed to patients or third-party payers. Must Have MCA
- * Option 3: Study is initiated and federally funded by a Government Sponsored Cooperative Group who will only pay for services that are solely conducted for research purposes and other protocol-required services (i.e., routine care services) will be billed to patients or third-party payers. Billing Grid Only Required, NO MCA
- * Option 4: Study involves only data collection and has no protocol-required clinical services. Does Not Need MCA
- * Option 5: Study is not described in any of the above options. Please describe the study and specify whether External Sponsor (i.e., industry, government, or philanthropic source) and/or patient/third party payer will pay for protocol required services. MCA MAY Be Required

Payment Option

Option 1

No MCA is needed per option selected above.

Payment Option 1:

- * Option 1A: Department/collaborating departments will act as internal sponsor paying for all protocol-required services and no protocol-required services will be billed to patients or third party payers.
- * Option 1B: Study involves protocol-required clinical services and an External Sponsor (i.e., industry, government, or philanthropic source) will pay for all protocol-required services.

Payment Option 1

Option 1B

24. Attachments

Туре	Name	Version	Status	Filename	Uploaded Date
Other - Other IRB Correspondance	RAVLT	1	New	RAVLT.pdf	02/23/2017
Package Insert Document (DRUG NAME)	strattera-pi.pdf	1	New	strattera-pi.pdf	02/26/2017

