- 2. Previous diagnosis or treatment for ADHD or any neurologic condition other than multiple sclerosis (e.g., traumatic brain injury, epilepsy)
- 3. clinical relapse of MS within 60 days of screening,
- 4. change in disease-modifying therapy within 90 days of screening,
- 5. below average estimated premorbid intelligence (WTAR score #16th percentile),
- 6. severe cognitive impairment indicated by a Mini Mental Status Examination (MMSE) < 24/30,
- 7. contraindications for atomoxetine use: (a) self-reported history of suicidal ideation within the last twelve months (Columbia Suicide Severity Rating Scale), (b) diagnosis of bipolar illness, (c) moderate or severe current depressive symptomatology (Beck Depression Inventory Fast Screen # 9), (d) diagnosis of hepatic disease, (e) narrow angle glaucoma, (f) pheochromocytoma, (g) monoamine oxidase inhibitor within 14 days of study drug start, (h) taking strong CYP2D6 inhibitors (e.g., paroxetine, fluoxetine, quinidine), (i) diagnosis of heart disease, (j) pregnant or planning pregnancy during the study period, (k) breastfeeding, (l) hypersensitivity to atomoxetine or component of formulation. Note that in the case where a potential subject is receiving medication for care that interacts with atomoxetine, her / his clinical regiment will not change to allow for study entry.

Enrollment Restrictions Based Yes
Upon Gender, Pregnancy,
Childbearing Potential, or Race

Justify Restriction(s)

We are excluded women who are pregnant or planning to become pregnant during the study period. Pregnancy risk associated with atomoxetine is category C (risk cannot be ruled out).

Age Range(s) 18 to 64 Years
Targeted Population(s) Adults - Patients

Other Aspects that Could Increase Subjects Vulnerability

None.

Safeguards to protect Subjects rights and welfare

We are employing inclusion / exclusion criteria which minimize risk to patients from atomoxetine, and we will monitor side effects. We will also emphasize the voluntary nature of this study, and that there is no penalty for withdrawal.

9. Subjects - Participation

Duration of an Individual Subjects Participation in the Study

Once consented and screened, the baseline will be completed and the rest of the study will take fourteen weeks: sixweek phase one, two-week washout, six-week phase two.

Duration Anticipated to Enroll All Study Subjects

One year

Estimated Date for the Investigators Within one year to Complete This Study

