Procedures for Subjects to Request Withdrawal

Subjects who desire to discontinue participation in this study will contact the study coordinator via telephone or email to withdraw.

The information collected prior to subject withdrawal may be used if deemed necessary to complete the study. As an FDA regulated study, the data cannot be destroyed. Data will not be distributed to anyone.

Procedures for Investigator to Withdraw Subjects

The investigator will withdraw subjects who fail to complete the baseline or follow-up evaluation, or who report serious side effects of the study medication as determined by Co-I [name] [name]. (attending MS neurologist).

The information collected prior to subject withdrawal may be used if deemed necessary to complete the study, unless the subject informs us in writing that they withdraw the data collected and the samples collected. Previously collected data can only be withdrawn if it has not yet been de-identified and distributed.

Participants Will Be Recruited Yes

Recruitment Method(s) Clinical Practice

How Participants Will Be Identified

Patients meeting inclusion criteria for age and MS diagnosis will be as asked by their treating physician, nurse practitioner, or neuropsychologist if they would be interested in hearing more about the study. If the patient is interested in participating and reports subjective difficulty with memory, a member of the research team will either speak with them in person, or they will be asked if they want to be contacted by a member of the research team at another time, or they will be given contact information for a member of the research team. If the patient is interested and would prefer to be contacted, the clinician will provide us with the name and best way to contact them. We also have a list of patients who have asked us to contact them if we have any enrolling research studies. We will contact those patients at their preferred contact.

Who Will Initially Approach Member of Primary Care Team, Treating

Potential Participants Physician
How Research Will Be Introduced to Participants

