After informed consent, subjects will engage in a 30-minute screening consisting of memory tests (Rey Auditory Verbal Learning Test, Visual Reproduction of the Wechsler Memory Scale, Fourth Edition), word-reading test (Weschler Test of Adult Reading), depressive symptoms (Beck Depression Inventory, Fast Screen), and assessment of suicidal ideation within the past twelve months (Columbia Suicide Severity Rating Scale).

Patients who meet all inclusion criteria will advance to the fourteen week crossover trial.

- 1. Baseline Evaluation:
- a. Memory Tests: Selective Reminding Test, Brief Visuospatial Memory Test, Revised, CANTAB Paired Associate Learning, NIH Toolbox Picture Sequence Memory Test (PSMT)
- b. Cognitive Efficiency Tests: Symbol Digit Modalities Test, CANTAB Rapid Visual Information Processing, Woodcock Johnson Reading Fluency, WAIS-IV Digit Span
- c. Questionnaires: Perceived Deficits Questionnaire (self-report of cognitive/memory deficits), Beck Depression Inventory, Fast Screen (mood), Fatigue Severity Scale (fatigue), Columbia Suicide Severity Rating Scale (suicidal ideation)
- d. Motor Tasks: 25-foot walk, Nine Hole Peg Test

2. Phase One Drug:

Patients will receive atomoxetine or identically encapsulated placebo from the research pharmacy. They will receive two containers: one containing seven 40mg capsules, and one containing enough 80mg capsules for the remaining five weeks. Subjects will be instructed to take the 40mg dose once per day (in the morning) for the first seven days, and then switch to the 80mg dose once per day (in the morning) for the remainder of Phase One. Subjects will be encouraged to set an alert in their smartphones to remind them to take the capsule at the same time each day. Subjects will also be provided with information about atomoxetine (Strattera) provided by the pharmaceutical company (Eli Lilly). Patients will be instructed not to take more than one capsule per day. If they miss a dose, they should keep it in the container. All remaining capsules will be returned to the investigator at the end of the six weeks (when the subject returns for the first follow-up). Patients will also be instructed to contact the study team immediately if they experience any side effects.

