3. Phase One Evaluation: The baseline evaluation will be repeated on the last day of Phase One. Alternate forms will be used as appropriate. In addition, patients will be asked to guess which type of capsule they were tasking, and also complete an additional questionnaire:

Patient-Reported Memory Change: Patients will endorse global memory change over the past month as: much improved (3), somewhat improved (2), mildly improved (1), unchanged (0), mildly worse (-1), somewhat worse (-2), much worse (-3).

4. Two week washout period.

Patients will go two weeks without taking any study capsule.

5. Phase Two Drug

The same procedures as Phase One will be followed, except that patients will receive the opposite capsules as Phase One.

6. Phase Two Evaluation

The same procedures as the Phase One Evaluation will be repeated.

Description of the Source Records that Will Be Used to Collect Data About Subjects

Paper source records will include demographic information, general medical history, and MS medical history information; however, there will be no PHI on any source forms. All data will be collected using paper neuropsychological record forms and/or score sheets. CANTAB tasks are performed on an iPad; however, no PHI will be entered into the iPad. Instead, CANTAB scores will be transferred to paper score sheets. All data will be entered into a RedCap database, which will include no PHI.

Description of Data that Will Be Collected Including Long-Term Follow-Up

This is documented above.

Research Requires HIV Testing

Page 15 of 32

11. Procedures - Genetic Testing

Genetic Testing Will Be Performed No
Guidance and Policies > Future Use Data Sharing and Genetic Research

Page 16 of 32

12. Procedures - Details

Surveys or Interviews Yes

Type of Instruments Being Used Standardized, Created By Research Team

Names of Standardized Instruments

NEUROPSYCHOLOGICAL INSTRUMENTS

Rey Auditory Verbal Learning Test

Visual Reproduction of the Wechsler Memory Scale

Brief Visuospatial Memory Test, Revised

Selective Reminding Test

CANTAB Paired Associate Learning

NIH Toolbox Picture Sequence Memory Test

Symbol Digit Modalities Test

CANTAB Rapid Visual Information Processing

Woodcock Johnson IV Reading Fluency

Wechsler Adult Intelligence Test, Third Edition: Digit Span

Wechsler Adult Reading Test

25-Foot Walk

Nine Hole Peg Test

QUESTIONNAIRES

Perceived Deficits Questionnaire

Beck Depression Inventory, Fast Screen

Fatique Severity Scale

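### Suicidal ideation is a named contraindication for atomoxetine, but withdrawal turns on 'severe' rather than 'serious' events and nothing visible ties phase two dispensing to ideation reported on study

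*Combined protocol and SAP*

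**What the plan says.** Section 8 (Exclusion Criteria, item 7) opens its list with "contraindications for atomoxetine use: (a) self-reported history of suicidal ideation within the last twelve months", measured by the C-SSRS. Section 10 (Description of Procedures Being Performed) places the eligibility decision after screening: "Patients who meet all inclusion criteria will advance to the fourteen week crossover trial". For phase two it says: "The same procedures as Phase One will be followed, except that patients will receive the opposite capsules as Phase One".

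Section 20 (Frequency of Data Review) sets the schedule: "Suicidal ideation will be evaluated at baseline, first follow-up, and second follow-up for all subjects". It promises immediate action if ideation is present, but refers back to the step already described, under which "Subjects who report suicidal ideation at any point in the study will be escorted to the psychiatric emergency department".

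There are two withdrawal rules. Section 9 (Procedures for Investigator to Withdraw Subjects) covers those "who report serious side effects of the study medication as determined by Co-I". Section 20 (Anticipated Circumstances of Subject Withdrawal) covers subjects with any 'severe' adverse event. Section 20 (Grading System) lists suicidal ideation and allergy to atomoxetine as 'serious' and a set of common symptoms as 'other'. Severity is a matter for the study physician, who "will review all adverse events as they are reported, and judge severity" and who may be unblinded to condition.

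**The concern.** In a crossover, the entry check protects the first period. A placebo-first subject takes a first dose of atomoxetine about eight weeks after phase one starts (six weeks of placebo plus two of washout), and nothing visible re-applies criterion 7(a) at that point. The plan does collect the relevant information, because the C-SSRS is given at the phase one evaluation, but it does not say what a positive result means for the next set of capsules.

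The withdrawal rules ought to fill that gap. Whether they do depends on one word. Ideation is on the 'serious' list, while withdrawal in section 20 is for 'severe' events. At stake is individual patient safety on the trial's own primary safety outcome: the rules as written may allow a drug to be given to someone who has just met a contraindication that the plan itself names.

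**Working it through.** The plan states no figure on this point. The check is a trace through the rules, then simple timing, then the cost of the fix.

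**Rule trace: placebo-first subject, first ideation reported at the phase one evaluation**

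1. Section 20, response to ideation: escort to the psychiatric emergency department. Required, but no instruction about study capsules.
2. Section 9, withdrawal: needs a serious side effect of the study medication. Not met if the event is judged unrelated. The reviewing physician may learn that it arose on placebo, and that same fact means the next capsules are atomoxetine.
3. Section 20, withdrawal: needs a 'severe' event. There are two readings:
   - Literal: severity is what the physician judges case by case, separately from the fixed 'serious' list. Not met if the event is not judged severe.
   - 'Severe' meant as 'serious': always met, because ideation is on the 'serious' list. The subject is withdrawn and the gap closes.
4. Section 10, phase two: opposite capsules after two weeks, with no stated eligibility or C-SSRS check.

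On the literal reading the path to atomoxetine is open. On the other reading it is closed at step 3. The literal reading also leaves no capsule rule for ideation reported at baseline, during phase one or during washout, in either sequence.

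**Timing on the literal path**

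- Phase one C-SSRS to first atomoxetine dose: 14 days (the washout). That is inside the twelve-month window of criterion 7(a), and also inside the six-month window given under How Participants Will Be Screened.
- Planned atomoxetine exposure: "Subjects will be instructed to take the 40mg dose once per day (in the morning) for the first seven days", then 80 mg for the remaining five weeks, so 7 + 35 = 42 days.
- Positive C-SSRS to next scheduled C-SSRS: 14 + 42 = 56 days, on the last day of atomoxetine.
- Placebo-first subjects: 12 of 24 if allocation is 1:1. The ratio is not stated, so this is an assumption.

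**Cost of a mandatory stop**

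Let r be the proportion of subjects reporting ideation before phase two dispensing. The documents give no value, so r is assumed. Expected pairs lost = 24r: 0.24 at 1%, 0.48 at 2%, 1.2 at 5%.

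Section 19 specifies paired t-tests but gives no power or effect size. Assuming 80% power and a two-sided 5% level, the noncentral t gives these detectable effects, in SDs of the paired difference:

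| Pairs | Detectable effect | Rise in standard error |
|---|---|---|
| 24 | 0.597 | reference |
| 23 | 0.611 | sqrt(24/23) - 1 = 2.2% |
| 22 | 0.626 | sqrt(24/22) - 1 = 4.4% |

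Power at 0.597 SD falls from 80% to about 78% and 76%. These figures describe the price of the fix, not the size of the risk.

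**The case against.** The strongest reply is that the plan already withdraws these subjects. Its grading section has only two tiers, 'serious' and 'other'. No 'severe' grade is defined anywhere, and section 9 states its withdrawal rule with 'serious'. The authors may well have used the words interchangeably. This stands as a plausible reading. It does not settle the matter, because severity is described as a separate judgement by the physician, and the section 9 rule adds a link to the study medication that the section 20 rule lacks.

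There are other safeguards. Ideation counts as a serious event in the 2:1 halting rule, and the physician reviews events as reported and can see the condition. Subjects are told to report side effects at once, so 56 days is the gap between scheduled C-SSRS assessments, not between contacts. Recent ideation and moderate or severe depression are excluded at entry. All of this lowers the chance of the open path being taken. But the halting rule works on the whole trial after twelve completers, and ideation on placebo would count on its placebo side. The physician could stop dosing, but no visible text requires it.

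A reader might infer that the escort is the only consequence of ideation, or that the plan would knowingly re-expose such subjects. The documents support neither inference: ideation feeds the halting rule and physician review, and it may already trigger withdrawal.

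Finally, a stop that ignores causality and severity displaces clinical judgement, and an atomoxetine-first subject would next have received placebo. That is a real cost. It is accepted because stopping only placebo-first subjects would reveal the sequence.

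**Conclusion.** The point holds as a conditional one. If 'severe' is read literally, the visible rules do not prevent a subject with new ideation, judged neither drug-related nor severe, from continuing to phase two. For a placebo-first subject with a positive phase one C-SSRS, that means starting a drug the plan calls contraindicated about two weeks later. If 'severe' was meant as 'serious', the plan already withdraws the subject and only the wording needs repair.

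It would go too far to conclude that contraindicated dosing is likely. That outcome needs new ideation, an emergency psychiatric evaluation that does not lead to a stop, a physician's judgement of neither drug-related nor severe, and dispensing that goes ahead anyway. With no ideation rate in the documents, no probability can be put on it.

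The conclusion is limited to the text available. The DMC document, the package insert and pages absent from the public file may contain provisions that close the gap. It remains worth correcting because it concerns the primary safety outcome and the correction is cheap under either reading.

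**What to change.** In section 20 (Anticipated Circumstances of Subject Withdrawal), change 'severe' to 'serious'. In section 9 (investigator withdrawal) and section 20 (items monitored for safety), state that any suicidal ideation reported before phase two dispensing, whether at baseline, during phase one, at the phase one evaluation or during washout, stops study capsules and bars further dispensing. The rule should apply in both sequences, whatever the causality or severity judgement.

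This takes a few sentences and uses C-SSRS results and event reports already collected, with no added visits or staff. The downside is the loss of the paired comparison for affected subjects, including atomoxetine-first subjects who would have moved to placebo. At the assumed rates that is about one pair or fewer on average. If 'severe' already means 'serious', there is little or no added loss.

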Patients will be asked by their physician, nurse practitioner, or neuropsychologist if they are interested in learning about a placebo-controlled RCT of a drug aiming to improve disease-related memory decline. Patients will be told that atomoxetine is a non-stimulant drug FDA-approved to treat ADHD, but that the use of atomoxetine to treat memory deficits is not an approved use of the drug. Patients will be told that it is a cross-over design, and that they will receive atomoxetine during one phase, and placebo during the other, but that he/she will not be blinded to phase. If they are interested, patients will be referred to the study personnel as noted above.

How Participants Will Be Screened

Inclusion and exclusion criteria will be reviewed with patients via telephone or in-person screening with study personnel. Patients who report memory difficulties and meet demographic eligibility criteria will be invited to the MS Center for a brief twenty-minute in-person screening. After informed consent, the screening will include two memory screening tests (RAVLT, WMS-IV Visual Reproduction), a word-reading estimate of premorbid IQ (WTAR), a depression screening tool (BDI-FS), and an assessment of suicidal ideation with the past six months (Columbia Suicide Severity Rating Scale). Demographic (e.g., age) and medical (e.g., last relapse) will be reviewed with the patient and/or their medical record. All current medications will be recorded, and Co-I [name] [name]. will review for possible interactions with atomoxetine.

10. Procedures - Narrative

Description of the Study Design

This is a double-blind randomized placebo-controlled cross-over design whereby each of 24 enrolled MS patients (meeting inclusion criteria / screening) will complete the following:

- 1. Baseline Evaluation (neuropsychological, psychological, self-report, and motor assessment; about 1 hour).
- 2. Phase One Drug: Six weeks of treatment with atomoxetine or placebo (randomly assigned)
- 3. Phase One Evaluation: baseline evaluation repeated on the last day of phase one.
- 4. Two week washout period
- 5. Phase Two Drug: Six weeks of opposite condition as phase one (i.e., if atomoxetine in phase one, then placebo in phase two)
- 6. Phase Two Evaluation: baseline evaluation repeated on the last day of phase one.

Description of Procedures Being Performed

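### The visible halting comparison is triggered by twelve completers, so withdrawals for severe or serious events postpone it

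*Combined protocol and SAP*

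**What the plan says.** Section 20 (Data - Safety Monitoring), under Rules for Alteration of Study Design, times the comparison of serious adverse events between conditions "After twelve subjects have been completed the trial". Its consequence is: "If serious adverse events are 2:1 more likely during atomoxetine, the study will be halted". The rule does not say whose events enter the comparison, whether withdrawn subjects count toward the twelve, or whether enrolment pauses. No calendar or enrolled-number trigger is given.

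Two passages take subjects out early. Section 20, Anticipated Circumstances of Subject Withdrawal: "Subjects would be withdrawn from the study if they experience any severe adverse events". Section 9, Procedures for Investigator to Withdraw Subjects, removes those "who report serious side effects of the study medication", as judged by the co-investigator, and also those who miss an evaluation. The grading text in Section 20 states: "Serious adverse events will include suicidal ideation and allergy to atomoxetine".

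On timing, Section 9 says that after baseline "the rest of the study will take fourteen weeks" and allows one year for enrolment. Section 10 describes "each of 24 enrolled MS patients", whereas the enrolment form in Section 7 gives 30.

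Section 20 also has the co-investigator review adverse events as they come in, with access to condition assignments. It lists a data monitoring committee file whose content is not among the documents.

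**The concern.** The trigger counts the subjects least likely to have been harmed. Anyone withdrawn for a severe or serious event before the end of phase two drops out of the count, and the twelfth completer must come from a later enrollee. The more often such withdrawals happen, the later the comparison meant to detect an excess of serious events on atomoxetine. Meanwhile enrolment continues, so more subjects start capsules before the rule can act. The primary safety outcome is suicidal ideation, so a rule that slows down as withdrawals for harm increase deserves correction even in a pilot.

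The point is about when the comparison is held. It does not depend on whether a 2:1 ratio is a good criterion.

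**Working it through.** The plan states the trigger (12 completers: 12/24 = 50% of the design sample, or 12/30 = 40% of the enrolment-form figure). It gives no calendar time to reproduce, so the timing is derived here.

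**Inputs from the documents**
- N = 24 (Section 10); 30 as the alternative (Section 7)
- Time from baseline to completion: 14 weeks (Section 9)
- Enrolment period T = 52 weeks (Section 9, one year)

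**Assumptions**
- Even enrolment: subject k starts at week k × T/N
- A fraction w is withdrawn before completing, spread evenly. No document gives w, so a range is shown.

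**Formulas**
- Twelfth completer is enrollee k = 12/(1 − w)
- Week of the comparison = k × T/N + 14
- Number enrolled by then = the smaller of N and week × N/T

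**Completer trigger, T = 52**

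| N | w | k | Week | Enrolled by then |
|---|---|---|---|---|
| 24 | 0 | 12 | 12 × 52/24 + 14 = 40.0 | 40 × 24/52 = 18.5 |
| 24 | 10% | 13.3 | 42.9 | 19.8 |
| 24 | 25% | 16 | 48.7 | 22.5 |
| 24 | 33% | 18 | 53.0 | 24 (enrolment over) |
| 30 | 0 | 12 | 12 × 52/30 + 14 = 34.8 | 20.1 |
| 30 | 25% | 16 | 41.7 | 24.1 |
| 30 | 33% | 18 | 45.2 | 26.1 |

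A simulation with random rather than even entry gave median weeks of 38.9 at w = 0 and 41.7 at w = 10% for N = 24, with median enrolment of 18 and 20. The pattern does not depend on perfectly even accrual.

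**Sensitivity to the accrual period.** Section 9 also expects the study to finish within one year. If that governs, enrolment must end by week 52 − 14 = 38. The no-withdrawal comparison is then at 12 × 38/24 + 14 = week 33, with 33 × 24/38 = 20.8 enrolled.

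**Enrolled is not the same as exposed.** Take N = 24, T = 52, and assume half the subjects get placebo first. At week 40:
- Not yet enrolled: 24 − 18.5 = 5.5.
- Placebo-first and still in phase one or washout (enrolled in the last 8 weeks): 8 × 24/52 × ½ = 1.8.
- Not yet exposed to atomoxetine: about 7.4 (summing before rounding).
- Currently taking it: two six-week windows, 2 × 6 × 24/52 × ½ = 2.8.

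At week 53, ignoring withdrawals, 7 × 24/52 × ½ = 1.6 are unexposed. About (5 + 6) × 24/52 × ½ = 2.5 are on drug.

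**Alternative trigger: first twelve to start capsules, each completed or withdrawn.** The twelfth starts at week 12 × 52/24 = 26 and is resolved by week 26 + 14 = 40 at the latest. Withdrawals can bring this forward but cannot delay it. With N = 30 the bound is week 34.8.

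**The case against.** The strongest reply is that safety oversight does not wait for twelve completers. The co-investigator sees events as they are reported, is told at once of serious ones, and can look up the condition. A cluster of serious events would reach an unblinded physician as it happened. The listed committee file may also hold further looks. This stands, and it limits the claim to the one halting comparison in the visible text. It does not remove the problem, because no study-level criterion is attached to the case-by-case review.

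Second, the larger delays rest on assumed withdrawal rates. Recent suicidal ideation, moderate or severe depressive symptoms and hypersensitivity to atomoxetine are exclusions, so withdrawals for the listed serious events may be few. At 10% the slip is about three weeks. This also stands. The direction follows from the text; the size does not.

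Third, not every serious event delays the look. Ideation is assessed at baseline and on the last day of each phase, so ideation first found at the phase-two evaluation occurs in someone who has already finished. The stated response to ideation is escort to emergency evaluation. Neither withdrawal passage says outright that every event defined as serious leads to withdrawal. A reader might infer that only subjects who tolerated both phases can count. The documents do not go that far.

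A reader might also infer that once all subjects are enrolled the rule protects nobody. In a crossover it does not follow: at that point some placebo-first subjects have not reached atomoxetine and others are still taking it.

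**Conclusion.** The concern holds for the formal comparison. Counting completers, while withdrawing subjects for severe events or serious side effects, makes the only halting comparison in the visible text later as such withdrawals rise. With 24 enrolled evenly over 52 weeks it moves from week 40 (no withdrawals) to about week 43, 49 and 53 at 10%, 25% and 33% withdrawn. With 30 it moves from about week 35 to week 42 at 25%. Even accrual and the withdrawal fractions are assumptions.

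A reader might go further and infer that the look may never take place. With 24 subjects, the binomial chance of fewer than twelve completers is 1.2% at 30% withdrawn and negligible at 10%. It becomes material only at rates for which the documents give no support. Nor do the documents show that the trial lacks safety oversight: event-level review is continuous, and the committee file could not be examined.

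**What to change.** In Section 20, Rules for Alteration of Study Design, replace the completer trigger. Hold the look when the first twelve subjects to start capsules have each either completed the trial or been withdrawn, and count serious adverse events in every subject who has taken a capsule by then. The number twelve, the reviewer and the 2:1 criterion stay as they are.

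The cost is about one sentence. The downside is that some of the twelve will contribute only one phase, so raw counts may reflect unequal time on each condition. Time on atomoxetine and on placebo should be shown beside the event counts.

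An additional look when the first twelve have finished phase one or been withdrawn is optional. It would come at about week 26 + 6 = 32, but would rest on a between-subject comparison of roughly six against six.

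The grounds for withdrawal, *severe* in Section 20 and *serious* in Section 9, must be reconciled with each other and with the serious-event definition. If the committee file contains other looks, Section 20 should refer to them.
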